10.1 Primary Efficacy Analysis

The primary analysis will estimate the absolute difference between each intervention arm and the control arm in the proportion of participants with periportal fibrosis adjusting for the baseline covariates;

- School (Buhirigi / Kaiso)
- fibrosis score (A, B) /(C,D, E, F)

- egg count epg
- duration of residency (2-4 years / > 4 years)

A generalised linear model with a binomial distribution and an identity link function will be fitted (12,13). Standard errors and 95% confidence intervals will be estimated directly from the model.

Should convergence issues arise with the identity link, then a model will be fitted with a logistic link to ensure convergence. The g-formula will then be used to provide an estimate of the average absolute risk difference (12,14). Specifically, for each participant a predicted probability for *all three* arms, but using their original covariate values will be calculated; the within-participant absolute difference calculated; the average of the differences across the participant population will be taken. Bootstrapping will be used to provide a standard error, 95% confidence intervals and p-values.

Hypothesis testing of the null (H0) against the alternative hypothesis (H1) will provide two-sided p-values for each of the three pairwise comparisons between the treatment arms.

H₀: there is no difference in the proportion of participants with periportal fibrosis between treatment arms.

H₁: there is a difference in the proportion of participants with periportal fibrosis between treatment arms.

The multiple testing procedure detailed in section 8.6 will be used whereby the p-value for the first hypothesis is compared to a significance level of 5 % if p< 0.05 then the null hypothesis is rejected and the α can be passed to the next hypothesis in the sequence (Fig 2).

A minimum 20% absolute difference in prevalence of periportal fibrosis between the control and intervention arms would be considered a clinically significant outcome. Based on preliminary data an incidence rate of scores C-F of 80% in the control arm is assumed.

10.2 Secondary Efficacy Analyses

10.2.1 Secondary analysis of primary endpoint

A secondary analysis of the primary endpoint will use a GEE (General Estimating Equation) approach (15,16). This will estimate the risk difference in the population adjusting for fibrosis score, epg and clustering by school to take account of any within-school correlation by "fitting' a model which assumes "exchangeable' correlations within schools and will also obtain robust standard errors. The GEE estimand is the risk difference at a population level, whereas it is the risk difference at the individual participant level for the primary analysis.

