6.1 General Study Design and Plan

(ICH E3; 9)

This is a phase IV, randomised superiority trial that is blinded to the primary outcome assessors, but open label to all other investigators and participants. The control arm is the standard annual dose of praziquantel, intervention arm 1 is a twice yearly dose of praziquantel and intervention arm 2 is a four yearly dose of praziquantel. Randomisation will be 1:1:1 to each arm and stratified by school.

Trial Flow Chart

pathological responses.

Blood sample collection for monitoring of host immuno-

NB! Only 120 participants sampled at 12 months and only parasitology egg counts and only pre-treatment.

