8.3 Covariates and Subgroups

(ICH E3; 9.7.1, 11.4.2.1. ICH E9; 5.7)

School site was used to stratify randomisation and will be adjusted for as a fixed coefficient in the primary analysis.

Baseline Fibrosis score and egg count will be fixed effects in the model.

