9.4.1 Demographics

- Age at enrolment: (years)
- Sex: (male/female)
- School: (Buhirigi / Kaiso)
- Class: (class 1, class 2, class 3, class 4)
- Residency in Hoima district: (2 years 4 years)

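### The GEE of the primary endpoint takes its robust standard errors from only two schools, so its intervals and p-values are not valid; the gatekept primary model is not affected

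*SAP*

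**What the plan says.** Section 10.2.1 describes one secondary analysis of the primary endpoint: a GEE for the risk difference, "adjusting for fibrosis score, epg and clustering by school to take account of any within-school correlation". It assumes exchangeable "correlations within schools and will also obtain robust standard errors". It names no small-sample correction, reference distribution or alternative variance. It justifies the analysis by a difference in target from the primary model: "The GEE estimand is the risk difference at a population level, whereas it is the risk difference at the individual participant level".

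The number of clusters is fixed elsewhere. Section 9.4.1 lists "School: (Buhirigi / Kaiso" as the only two levels, and section 10.1 uses the same two. On the design, section 6.1 states: "Randomisation will be 1:1:1 to each arm and stratified by school". Section 6.3 makes clear that the allocation attaches to the individual child's identification number. Section 8.3 says how school enters the primary model: "School site was used to stratify randomisation and will be adjusted for as a fixed coefficient in the primary analysis".

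**The concern.** Robust (sandwich) standard errors are justified by having many independent clusters. With two, the variance of an arm effect is estimated from a single contrast: how far the two schools' effects happen to differ. If they agree by chance, the standard error collapses towards zero and the result looks highly significant. If they differ by chance, a real effect is hidden.

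The clustering is also not needed. Children are randomised within school, every arm is present in each school, and arms are compared within school. School is a stratum, and the primary model already treats it as one.

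What is at stake is interpretation. The GEE will be read as confirming or contradicting the primary result, and with this variance it can do neither.

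**Working it through.** **Inputs**
- Clusters: G = 2 (sections 9.4.1 and 10.1).
- Randomisation: by child, 1:1:1 within school (sections 6.1 and 6.3).
- Model: intercept, two arm terms, baseline fibrosis and epg, so 5 coefficients (section 10.2.1). The link is not named; identity is assumed because the target is a risk difference.
- Level: 5% two-sided, carried over from sections 8.6 and 10.1. Section 10.2.1 states none.
- Size: 100 per arm (section 7), 300 in total.
- Not in the SAP, hence assumed: the split between schools (50:50, varied from 20:80 to 65:35), an uncorrected sandwich and a normal reference.

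**The plan's own figure.** The SAP gives no error rate for the GEE. The nearest stated figure is 88% power for 80% vs 60% with 100 per arm. Power = Φ[(0.20 − 1.96·√(2·0.7·0.3/100)) / √((0.16 + 0.24)/100)] = Φ[(0.200 − 0.127)/0.0632] = Φ(1.154) = 87.6%. It reproduces.

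**Step 1: rank.** At the GEE solution the two school score totals sum to zero, so u₂ = −u₁. The middle matrix of the sandwich is u₁u₁ᵀ + u₂u₂ᵀ = 2u₁u₁ᵀ, which has rank 1 for 5 coefficients. This needs no assumption about the split or prevalence, and it held in every simulated fit.

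**Step 2: closed form, equal schools, no effect.** Let b₁ and b₂ be the arm effects in the two schools, each with variance σ².
- Estimate: (b₁ + b₂)/2. Sandwich SE: |b₁ − b₂|/(2√2).
- z = √2·(b₁ + b₂)/|b₁ − b₂|, which is √2 times a standard Cauchy variable.
- P(|z| > 1.96) = 1 − (2/π)·atan(1.96/√2) = **39.8%**.
- Robust SE over true SE (σ/√2) = |Z|/√2 with Z standard normal. Its median is 0.674/1.414 = 0.48, and its 95th percentile is 1.96/1.414 = 1.4.

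**Step 3: corrections the SAP does not name.**
- G/(G−1) = 2 multiplies the SE by √2: 1 − (2/π)·atan(1.96) = **30.0%**.
- That correction plus t on 1 df (critical value 12.71) gives 5%. Power for 80% vs 60%: the variance per school is 0.16/50 + 0.24/50 = 0.008, the SE of the average is √(0.008/2) = 0.0632, and 0.20/0.0632 = 3.16. Power is about √(2/π)·3.16/12.71 = 0.20, so **about 20%** against the planned 88%.
- A bias-reduced sandwich with a normal reference rejected in 21.6% of 500 null trials.

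**Step 4: null simulation of the GEE** (3,000 to 4,000 trials per setting).

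| School split | False positives per comparison |
|---|---|
| 50:50 (N 300 or 450; prevalence 20–30% or 70–85%) | 39–41% |
| 35:65 | 40–41% |
| 65:35, prevalence 70% and 85% | 42–44% |
| 20:80 | 46–48% |

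At least one of the three pairwise tests was falsely significant in 74–81% of trials.

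**Step 5: fibrosis rare in one school.** Section 9.3.3 reports that very few participants had fibrosis in the 2020 data, which section 9.3 identifies as Buhirigi. Take 1% there and 40% in Kaiso (assumed values), 400 null trials per setting. The GEE rejected in 14% (Buhirigi:Kaiso 200:100), 24% (150:150) and 63% (100:200). A separate repeat gave 20%, 20% and 60%.

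**Step 6: the alternative.** With school as a fixed effect and child-level robust SEs, the same kinds of null data gave about 3–6%. The repeat of the rare-fibrosis settings gave 5–8%, the highest value arising where only 100 children came from Kaiso. GEE with model-based SEs gave 6.2% in the one setting tried (500 trials).

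**The case against.** **The 40% is not a property of the plan.** This is right. Section 10.2.1 names no test, level, reference distribution or package, and section 14 says only R 4.1.1. The school split is not given either. A reader might infer a flat 40% error rate; the documents support only a conditional figure. The conclusion does not depend on it: rank 1 follows from two clusters alone, and the corrected versions in step 3 either over-reject or lose most of the power.

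**The trial's confirmatory result is not touched.** This also stands. Inference on the primary endpoint is the gatekept sequence of section 8.6 applied to the model of section 10.1, which "will provide two-sided p-values for each of the three pairwise comparisons between the treatment arms" with school as a fixed term. The GEE carries no alpha. A reader might infer that the primary result is compromised; it is not. Nor is the GEE the only supporting analysis: there are also the missing-data sensitivity analysis (8.4), CACE (10.3.1) and the best-case/worst-case datasets (16.1.7).

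**The estimand sentence.** A reader might infer that it is simply false because the g-formula in section 10.1 already averages over participants. That goes too far. The g-formula is a fallback for non-convergence, and the planned estimate is the identity-link coefficient. Individual-level and population-level risk differences coincide if the effect is constant across covariates. If it differs by school they need not, and section 10.2.2 itself adds a post hoc treatment-by-school interaction for infection intensity. What stands is that the contrast does not hold as a general statement.

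**Deleting the GEE.** The SAP already records post hoc decisions (9.3.3, 10.2.2, 16.1.5). Dropping a planned analysis without a record would invite a charge of selective reporting. A logged change of variance method avoids that.

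**Conclusion.** Wrong as written, and a should-fix. The standard errors, intervals and p-values planned in section 10.2.1 rest on a rank-1 variance from two schools and cannot be used.

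The size is conditional. With an uncorrected sandwich and a normal reference, the false-positive rate is about 40% at an assumed equal split, and from about 15% to over 60% depending on the split and on how rare fibrosis is in one school. It is about 30% with G/(G−1). It is 5% with that correction and a 1-df t, at about 20% power in the plan's own 80% vs 60% scenario.

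The fixed-school model of section 10.1 does not share the fault.

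**What to change.** 1. In section 10.2.1, drop clustering on school from the variance. Adjust for school as a fixed effect, as section 8.3 already does, and use child-level heteroscedasticity-robust or bootstrap standard errors. A logistic g-formula risk difference or a linear-probability model would both serve. If bootstrapping, resample children within school.
2. Reword the estimand sentence to say that, with an identity link and a constant effect, the individual-level and population-level risk differences coincide.
3. Record the change and its reason in section 16. If the GEE has already been run, do not rely on its standard errors, intervals or p-values.

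The cost is a few lines of SAP text and a short change to the program. No new data are needed, and the primary analysis and testing sequence stay as they are.

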10.2.2 Analysis of secondary endpoint – Infection intensity (mean epg)
Analysis of the secondary endpoint will test if there is a difference in the mean infection intensity between the control and each intervention arm as well as between each of the two intervention arms.

A multiple linear regression model will estimate the infection intensity at 24 months for each treatment group adjusted for baseline infection intensity (EPG), and school. A z-test will compare each of the three pairwise comparisons separately and provide a p-value for the probability that a difference in the means produced by the model would be observed purely due to chance.

Note that an additional analysis was added post hoc which modelled the mean infection intensity by treatment group which adjusted for baseline infection intensity and school with an interaction term between treatment group and school.

10.2.3 Analysis of secondary endpoint – Infection intensity (Heavy infection)

An additional analysis of the infection intensity endpoint will be conducted by dichotomising EPG into ≥400 EPG or <400 EPG relating to 'heavy infection' and 'not heavy infection'. The analysis will estimate the proportion of 'heavy infection' for each treatment arm by fitting a logistic regression model and adjusting for baseline infection intensity (epg), and school. 95% confidence intervals for the proportions will be estimated using the standard error from the model.

10.2.4 Analysis of secondary endpoint - Egg Reduction Rate

A mixed model repeated measures analysis with an unstructured covariance matrix for the within - patient residual errors will estimate the Egg Reduction Rate (ERR) between:

- o baseline and 24 month +4 weeks
- baseline and baseline + 4 weeks
- o 24 months and 24 months + 4 weeks

for each treatment group using log transformed epg counts at 3 time points (baseline +4 weeks, 24 months and 24 months + 4 weeks). The model will specify fixed effects of treatment, time and baseline epg count with an interaction term between treatment and time. A weight argument will allow a distinct variance for each time point. The treatment effect coefficient (βx) in this model quantifies the relative change and the ERR is given by $1 - \exp(\beta x)$.

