6.3 Randomisation and Blinding

(ICH E3; 9.4.3, 9.4.6, ICH E9; 2.3.1, 2.3.2)

Prior to enrolment trial participant identification numbers will be generated and these numbers assigned an intervention arm via simple computer generated random number randomisation. This paper-based list will be provided to the trial site team and upon enrolment children will be assigned to the ordered participant identification numbers, class-by- class and school-by-school and school-by-school or household-by- household if schools are not open. Randomisation will be stratified by school. The trial is open label to participants and the investigators, with the exception of the ultra-sonographers who are undertaking the scoring for the primary trial outcome. Scoring will be undertaken remotely from the participant being examined and the technicians conducting the exam.

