9.3 Protocol Deviations

All school-based trial activities were paused on 19th March 2020 in accordance with the Ugandan government announcement concerning COVID-19. Therefore, baseline data for the trial had been collected at different time-points.

Baseline data collected from Buhirigi was collected 17 months after MDA, in March 2020, Baseline data for Kaiso was collected 9 months after MDA, in March 2021.

In order to ensure data integrity a 10% resample of the Buhirigi baseline data was performed in March 2021 for the primary and secondary endpoints.

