11.1.3.2 Exploratory analysis of Adverse Events and Infection Intensity: Logistic regression

A further exploratory analysis will model the log odds of any adverse event using infection intensity (epg) on a continuous scale, treatment, and age group as

predictors. Exposure variables will be modelled as fixed effects with an interaction term between infection intensity and age group.

Logistic regressions for both baseline and 24 month time points will be performed.

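### The egg reduction rate model in SAP 10.2.4 omits school, the stratification factor that the primary and other modelled egg-count analyses adjust for; adding it is a minor, nearly free improvement

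*SAP*

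**What the plan says.** Section 6.3 states: "Randomisation will be stratified by school". Section 8.3 says how school enters the analysis: "School site was used to stratify randomisation and will be adjusted for as a fixed coefficient in the primary analysis". That commitment covers the primary analysis only, but the SAP's other models follow the same practice:

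- Section 10.1 (primary endpoint) lists school among the covariates.
- Section 10.2.2 (mean epg at 24 months) is "adjusted for baseline infection intensity (EPG), and school", and a treatment-by-school interaction was added post hoc.
- Section 10.2.3 (heavy infection) and section 10.2.5 (prevalence) also include school.

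The ERR model in section 10.2.4 does not. It is fitted "using log transformed epg counts at 3 time points (baseline +4 weeks, 24 months and 24 months + 4 weeks"), and its terms are given in full: "The model will specify fixed effects of treatment, time and baseline epg count with an interaction term between treatment and time". No reason is given for leaving school out.

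On baseline timing, section 9.3 says: "Baseline data collected from Buhirigi was collected 17 months after MDA, in March 2020". For the other school: "Baseline data for Kaiso was collected 9 months after MDA, in March 2021".

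ERR is listed as an exploratory objective (5.1.3) and an exploratory endpoint (5.2.2), although the heading of 10.2.4 calls it secondary.

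**The concern.** When randomisation is stratified on a factor that predicts the outcome, a model without that factor puts the between-stratum variation into the residual. The reported standard errors of arm contrasts are then too large.

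There is a particular reason to expect school to matter here. Baseline epg is the model's only adjustment for differences between children, and it was measured in different years and at different intervals after mass treatment. Section 15.1.1 also records a delay between Buhirigi's first collections and its first dosing. One baseline slope with no school term assumes that equal baseline counts in the two schools predict equal later counts.

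A second consequence concerns the ERR reported for each arm, as distinct from the comparison of arms. That is a change over time within an arm, and stratified randomisation does not protect it. If the school mix of observed children changed between visits, a model without school would attribute part of the school difference to time.

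**Working it through.** **Inputs.** The SAP gives no power, SD, school size or school-level egg count for ERR, so there is no stated figure to reproduce. The following are assumptions: half the children in each school (q = 0.5), and a school effect *d* in residual SDs of log epg, after adjustment for baseline epg.

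**Step 1: standard error of an arm contrast.** In a linear model with arms balanced within school, omitting school multiplies the standard error by √(1 + d²·q(1−q)). With q = 0.5, q(1−q) = 0.25.

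| d (residual SDs) | Calculation | Increase in SE |
|---|---|---|
| 0 | √1 | 0% |
| 0.25 | √(1 + 0.0625 × 0.25) = √1.0156 | 0.8% |
| 0.5 | √(1 + 0.25 × 0.25) = √1.0625 | 3.1% |
| 1 | √(1 + 1 × 0.25) = √1.25 | 11.8% |

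**Step 2: the same question in the planned model.** The 10.2.4 model (three visits, unstructured covariance) was simulated with 100 children per arm, 150 per school, residual SD 2, correlation 0.4 between visits, 30% missing at each visit in both schools, no true arm effect, and 150 runs per scenario. For the 4x versus 1x contrast at 24 months:

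- d = 0.5: mean model SE 0.336 without school and 0.327 with it (0.336/0.327 = 1.03).
- d = 1: mean model SE 0.357 without school and 0.325 with it (0.357/0.325 = 1.10).

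This agrees reasonably with step 1. With exact balance of arms within schools, the actual spread of the estimates hardly changed (0.329 without school and 0.323 with it at d = 1). The fault is therefore mainly that uncertainty is overstated.

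**Step 3: bias in arm contrasts.** Over six scenarios, three of them with missingness that differed by school, the mean contrast without school lay between −0.039 and 0.024, against a true value of 0. The simulation error of such a mean is about 0.34/√150 = 0.028. There is no sign of bias.

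**Step 4: within-arm ERR.** Of the three ERRs in 10.2.4, only 24 months to 24 months + 4 weeks lies between two modelled visits, because baseline is a covariate. The true log change was set at −2.5, so the true ERR is 1 − exp(−2.5) = 91.8%. Missingness over the three visits was set deliberately unequal: 50/10/30% in one school and 10/50/50% in the other.

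| School gap in log epg | No school | School | School and school-by-time |
|---|---|---|---|
| 1 at every visit | 91.6% | 91.9% | 91.9% |
| 2 at every visit | 91.0% | 91.5% | 91.5% |
| 2 at 24 months only | 89.2% | 89.6% | 92.1% |

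With equal missingness in the two schools, all three models gave 91.7% to 92.1%. A shift therefore needs both a school effect and a change in school mix. Where the school gap varies by visit, a school main effect alone does not remove it.

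**The case against.** The strongest reply is that the SAP breaks no rule of its own. Section 8.3 promises school adjustment for the primary analysis only, and ERR is exploratory. That stands: this is an inconsistency with the neighbouring models and not a contradiction.

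A second reply is that the baseline timing is partly handled. Baseline epg is in the model, and sections 9.3 to 9.3.2 plan a Buhirigi resample to check the older counts. That also stands in part. The resample can show whether the counts drifted, but it does not put school into the ERR model.

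Four stronger readings are tempting, and the SAP does not support them:

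- **School-specific attrition distorts ERR.** A reader might infer this from section 7. The only loss tied to one school there is missing consent documentation, affecting around 25% of that school's participants. Section 8.2.1 removes anyone not re-consented from the Full Analysis Population, so they are absent from every visit and do not by themselves change the mix between visits. Relocation, flooding and lost livelihoods are not attributed to either school. The unequal missingness in step 4 is an assumption.
- **Arm comparisons are biased.** Randomisation was stratified by school, and step 3 found no bias.
- **Standard errors could be inflated by 20%.** That needs a school gap of 2 log units against a residual SD of 1.5, or 2/1.5 = 1.33 SD, remaining after baseline adjustment. Nothing in the SAP points to a gap of that size.
- **The adverse event model in 11.1.3.2 has the same defect.** It also lists no school term, but section 5.1.3 sets a prediction aim for that work, for which a pooled analysis is legitimate. The SAP offers nothing from which to size an effect.

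**Conclusion.** The point holds as a minor one. The ERR model omits a stratification factor that the trial already records and that the primary, mean-epg, heavy-infection and prevalence models all use, and no reason is given.

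The expected cost is standard errors about 1% to 12% too large for arm contrasts. This rests on equal school sizes and a school effect of 0.25 to 1 residual SD beyond baseline epg. The cost is zero if school adds nothing once baseline epg is known.

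A shift in within-arm ERR is possible but conditional. It was under one percentage point in the simulation when the school gap was constant, and about 2.6 points (91.8% to 89.2%) when the gap existed at 24 months only, both under deliberately unequal missingness. The SAP gives no school-level data that would show or exclude this. The primary result is not affected.

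**What to change.** In section 10.2.4, add school and school-by-time as fixed effects. School-by-time is needed because a main effect alone did not correct the ERR when the school gap varied by visit. Report each arm's ERR averaged over the school mix as randomised, so that every visit refers to the same population.

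Sections 9.3.3 and 16.1.5 already record decisions and analyses made post hoc. If data have been seen, list this change in 16.1.5 with the same label and show the model as now specified beside it.

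With two schools and three modelled visits, the cost is 1 + (2 − 1)(3 − 1) = 3 degrees of freedom. No new data are needed.

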9.1.2 Consort Flow Diagram

9.2 Derived variables

Periportal Fibrosis is a binary outcome:

WHO ultrasonography Niamey protocol pattern scores of C, D, E or F=1 (i.e. has periportal fibrosis)

WHO ultrasonography Niamey protocol pattern scores of A or B=0 (i.e. does not have periportal fibrosis)

Kato-Katz egg counts

o Eggs Per Gram

The epg value for each participant visit is calculated in the macro database as the mean of the kato-katz slide egg counts from a maximum of 3 stool samples multiplied by an adjustment factor (one stool sample is sufficient for protocol adherence at a particular time point).

Helminth distributions within the human host are highly over dispersed therefore the epg values for each participant will be log transformed using natural logs (In).

A constant value of 1 will be added to all raw epg values to allow for the possibility of an epg value of 0.

$$\sum (\ln(epg+1))$$

The geometric mean epg will be calculated as below:

$$e^{\frac{\mathcal{E}(\ln(epg+1))}{n}} - 1$$

95% Cl's calculated on the logarithmic scale can also be converted back to the original scale by exponentiating and subtracting 1.

Egg Reduction Rate (ERR)

Sample Egg Reduction Rate will be estimated as:

$$(1-(epg2 \div epg1) \times 100)$$

Where epg1 and epg2 are the arithmetic mean of epg of faeces at:

- baseline and at 24 months + 4 weeks
- baseline and baseline + 4 weeks
- o 24 months and 24 months +4 weeks

o **Heavy Infection**

The WHO classifies 'Heavy infection' as those with epg counts of \geq 400. Where the percentage of children with of heavy infection is < 5% then morbidity control is considered to have been achieved and if the percentage of heavy infection is < 1% then the disease is considered to have been eliminated as a public health concern.

Heavy Infection: Binary variable $-1 = "yes" = epg \ge 400$, 0 = "no" = epg < 400 or not detectable

Disease status

Disease status is a binary variable where 0 = No disease (epg =0); 1 = Disease (>0 epg)

Point Prevalence (PP)

Is a measure of disease frequency and quantifies the proportion of individuals in a population who have Schistosomaisis mansoni at a specific instant in time.

$$PP = \frac{Total\ number\ of\ participants\ who\ have\ an\ average\ epg > 0}{Total\ number\ of\ participant\ at\ risk}$$

Total number of participants at risk will include all participants for whom at least one stool sample was collected at the timepoint being assessed.

Cure Rate (CR)

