9.5 Treatment Compliance

Information relating to the number of participants who missed the IMP at the required visit captured in the 'Non-Adherence to protocol' CRF as well as the 'IMP administration' CRF will be shown in a summary table and displayed as a stacked bar chart, each treatment group represented by their colour and position within the stack. The number missing will be a scale on the y axis and each treatment time—point will be ordered on the x axis.

- · Standard of Care Arm: Baseline, 12 months and 24 months
- Intervention Arm 1 (2 x treatment): Baseline, month 7, month 12, month 19 and month 24
- Intervention arm 2 (4 x treatment): Baseline, month 4, month 7, month 10, month 12, month 16, month 19, month 22 and month 24

Information relating to the number of participants who missed data collection visits captured in the 'Non-Adherence to protocol' CRF will be shown in a summary table and displayed using a stacked bar chart with each treatment arm represented by their colour and position within the stack, the number missing will be shown on the y axis and time-point on the x axis.

- Ultrasonography
- Parasitology
 - Standard of Care Arm: Baseline and 24 months
 - o Intervention Arm 1: Baseline and 24 months
 - o Intervention arm 2: Baseline and 24 months

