10.2.5 Analysis of secondary endpoint - Prevalence of infection

The burden of disease will be estimated by calculating the prevalence at 24 months. A binary variable indicating disease status will be created and each participant will be classed as either having Schistosomaisis or not using the average EPG at 24 months.

No Disease 0 = EPG = 0

Disease 1 = EPG > 0

A logistic regression model will be fitted to estimate the prevalence odds ratio adjusted for age, sex and school.

Note that an additional analysis was included post hoc which modelled prevalence of infection at 24 months adjusting for baseline $\ln(epg+1)$, age, sex and school.

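### The egg reduction rate model gives baseline egg count one slope for all three visits, so the 24 months to 24 months + 4 weeks rate receives no baseline adjustment

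*SAP*

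**What the plan says.** SAP section 10.2.4 plans "A mixed model repeated measures analysis with an unstructured covariance matrix for the within - patient residual errors". The responses are "log transformed epg counts at 3 time points (baseline +4 weeks, 24 months and 24 months + 4 weeks"), so baseline is a covariate and not a response. The mean model is fixed in one sentence: "The model will specify fixed effects of treatment, time and baseline epg count with an interaction term between treatment and time". Treatment by time is the only interaction named, and no baseline-by-time term appears elsewhere in the SAP. A separate variance is allowed at each visit.

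The model is to deliver three ERRs per arm: baseline to baseline + 4 weeks, baseline to 24 months + 4 weeks, and 24 months to 24 months + 4 weeks.

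Sections 5.1.3 and 5.2.2 list ERR as exploratory, while the title of 10.2.4 calls it secondary. Section 8.4 assumes data are missing at random.

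**The concern.** A reader of 10.2.4 would take all three ERRs to be adjusted for baseline egg count. One is not. A covariate with the same coefficient at two visits contributes nothing to the difference between them.

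The SAP lets variances and covariances differ freely by visit but holds the baseline slope constant, without giving a reason. The visits are not alike. Baseline + 4 weeks follows one scheduled dose in every arm. By the 24-month visit, the schedule in section 9.5 has given the 4x arm seven further doses ("Baseline, month 4, month 7, month 10, month 12, month 16, month 19, month 22 and month 24", not counting the first and last), the 2x arm three and the control arm one. The last visit again follows a dose. Equal baseline slopes at all three visits are possible, but nothing in the SAP makes them likely.

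At stake is some precision for one of the three ERRs. If children with higher or lower baseline counts are lost more often, protection against bias in that ERR is also at stake.

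**Working it through.** The SAP states no figure for this model, so there is none to reproduce. It supplies the model terms and visits (10.2.4) and 100 children per arm (sections 7 and 16.1.1). All SDs, slopes and correlations below are assumptions.

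**Step 1: cancellation.** Let x be baseline and t2, t3 the 24-month and 24 months + 4 weeks visits. As written, E[Y_t] = μ(arm, t) + b·x. Then E[Y_t3 − Y_t2] = μ(arm, t3) − μ(arm, t2), and b·x is gone. In one simulated complete data set the fitted changes in the three arms were −2.30702, −2.30008 and −1.95393. These equalled the raw mean changes to more than 10 decimals.

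**Step 2: cost in precision, complete data.** With visit-specific slopes, the model removes (b3 − b2)²·σx² from the variance of the change. The variance ratio for a between-arm contrast, common slope against visit-specific slopes, is raw variance / (raw variance − amount removed).

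*Assumption set A.* SD of ln(epg+1) is 2.2 at baseline, 2.1 at 24 months and 1.7 at + 4 weeks; correlation between follow-up visits is 0.45. Since b = r·SD_t/2.2, the amount removed is (1.7·r3 − 2.1·r2)². Raw variance = 2.1² + 1.7² − 2(0.45)(2.1)(1.7) = 4.41 + 2.89 − 3.213 = 4.087.

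| Baseline correlation at the three visits | Removed | Ratio |
|---|---|---|
| 0.5 / 0.2 / 0.1 | (0.17 − 0.42)² = 0.063 | 4.087/4.024 = 1.016 |
| 0.5 / 0.3 / 0.2 | (0.34 − 0.63)² = 0.084 | 4.087/4.003 = 1.021 |
| 0.3 / 0.4 / 0.3 | (0.51 − 0.84)² = 0.109 | 4.087/3.978 = 1.027 |
| 0.2 / 0.5 / 0.2 | (0.34 − 1.05)² = 0.504 | 4.087/3.583 = 1.141 |
| 0.1 / 0.5 / 0.1 | (0.17 − 1.05)² = 0.774 | 4.087/3.313 = 1.234 |

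*Assumption set B.* Baseline SD is 1.8, residual SDs 1.6 and 1.2 at the last two visits, and residual correlation ρ 0.2 to 0.5. The ratio is 1 + 3.24(b3 − b2)²/(4.00 − 3.84ρ).

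| Slopes at the three visits | 3.24(b3 − b2)² | Ratio, ρ = 0.2 to 0.5 | Simulated (300 trials) |
|---|---|---|---|
| 0.3 / 0.3 / 0.3 | 0 | 1.00 | 1.00 |
| 0.5 / 0.2 / 0.1 | 0.032 | 1.01 to 1.02 | 1.01 |
| 0.3 / 0.5 / 0.2 | 0.292 | 1.09 to 1.14 | 1.10 to 1.14 |
| 0.2 / 0.6 / 0.1 | 0.810 | 1.25 to 1.39 | 1.25 to 1.39 |

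Confidence-interval width grows with the square root of the ratio: √1.021 = 1.01, √1.141 = 1.07, √1.389 = 1.18.

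**Step 3: bias, complete data.** Neither model showed bias beyond simulation error, and the model-based standard errors were close to the simulated SDs for both.

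**Step 4: bias, incomplete data.** About 30% loss to follow-up was simulated, rising with baseline count, under set B with ρ = 0.3. The bias in a within-arm change is roughly (b3 − b2) × (mean baseline of those seen − mean baseline of all).

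- Slopes 0.5/0.2/0.1: bias in the log change was about 0.02 to 0.05 with the common slope. With baseline-by-time it was at most about 0.02.
- Slopes 0.2/0.6/0.1: bias was about 0.2 with the common slope and about 0.01 or less with baseline-by-time. The true change in the 4x arm was −1.8, an ERR of 1 − exp(−1.8) = 83.5%. The common slope gave about 1 − exp(−1.59) = 79.6%.
- Loss tied to baseline in the 4x arm but not the control arm, slopes 0.2/0.6/0.1: the between-arm difference in change was biased by 0.22 with the common slope and 0.01 with baseline-by-time. With slopes 0.5/0.2/0.1 the figures were 0.06 and 0.04, against a simulation error of about 0.27/√300 = 0.016.

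**The case against.** The strongest reply is that this is an efficiency choice and not an error. The third ERR compares two counts 4 weeks apart in the same child, with the 24-month count as its reference. Leaving it unadjusted for a count taken two years earlier is valid, and randomisation protects the arm contrasts. Section 10.2.4 estimates ERR per arm and states no test or power for it. With complete data all of this stands.

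The gain may also be negligible. Baseline + 4 weeks is the visit closest to baseline, so a correlation that decays over time is at least as plausible as one that peaks at 24 months, and the cost is then about 2%. Section 9.3 adds to the uncertainty about these correlations: "Baseline data collected from Buhirigi was collected 17 months after MDA, in March 2020", whereas Kaiso's was collected in March 2021. This also stands, and it is why the size can only be given as a range.

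A reader might go further and infer that the model uses the wrong slope at 24 months, too shallow for that visit. The SAP does not support this. It gives no slopes, and the direction depends on the assumption. Under set A the common slope is 0.249 against 0.477 at 24 months for correlations 0.2/0.5/0.2, but 0.260 against 0.191 for 0.5/0.2/0.1. Nor is the 24-month level an output of this model. It enters only the change from which the slope cancels, and the arm comparison at 24 months is a separate regression with its own baseline slope (10.2.2).

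Two further remarks are fair. Adding the interaction makes each arm's change depend on the baseline value, so that value must be stated. And the term does not settle a separate question in the same section: "The treatment effect coefficient (βx) in this model quantifies the relative change", yet with baseline as a covariate a treatment coefficient compares arms rather than visits, and section 9.2 defines ERR differently ("Where epg1 and epg2 are the arithmetic mean of epg of faeces at", followed by the visit pairs).

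**Conclusion.** The point holds in a limited form. As written, the model gives baseline one slope, and with complete data the 24 months to 24 months + 4 weeks ERR is unadjusted for baseline. That follows from the stated terms and needs no assumption.

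The size does rest on assumptions. The variance of the between-arm contrast in that change is inflated by 0% with equal slopes, about 2% with decaying correlation, and 14 to 23% when the 24-month count is much more closely tied to baseline. The most extreme case tried reached 39%.

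A reader might infer that the planned estimate is biased. With complete data it is not. With loss related to baseline count it can be: baseline is then one of the variables on which missingness depends, and the change needs its own baseline term for the missing-at-random assumption to protect it. The SAP does not show that loss follows this pattern. Section 8.4 records a planned 25% loss, and section 7 describes further tracing problems, so it cannot be ruled out.

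The weight is minor: one interval of an endpoint listed as exploratory, improved at almost no cost.

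**What to change.** In section 10.2.4, add a baseline-by-time interaction. Enter baseline as ln(epg+1), the scale of the outcome; the present text says only baseline epg count, whereas the added analysis in 10.2.5 ("modelled prevalence of infection at 24 months adjusting for baseline") already uses ln(epg+1). Centre it at the overall baseline mean, and obtain each arm's between-visit changes as marginal means at that common value. Without centring, the time coefficients would refer to a child with zero eggs at baseline. Keep treatment, time, treatment-by-time and the unstructured covariance.

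The cost is two extra parameters (three slopes instead of one) in about 300 children, a sentence or two of SAP text, and a small change to the code, including the marginal-means step. No new data are needed. The SAP already records post hoc additions in section 16.1.5. If outcome data had been seen when this term is added, list it there as a supplementary analysis beside the model as written.
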